1.3. Schedule of activities (SoA)

Table 1 Study activities for retrospective cohort

Type of contact	Visit 1/Contact 1	Notes
Timepoint	Day 1 ^c	
Participant Contact ^a	•	
Informed consent	•	Maternal and infant informed consent
Inclusion and exclusion criteria	•	
Demography and lifestyle characteristics	•	Mothers: Demography at enrollment, and lifestyle during or at the end of each pregnancy Infants: Demography at birth, and lifestyle at Day 42 post-delivery
Medical and vaccination history	•	Collect information prior to start of study pregnancies (for each pregnancy)
Contact information for all HCPs seen by mother or infant from start of current study pregnancies through day 42 post-delivery	○	
Safety assessments during current study pregnancies (from medical record review)		
Record concomitant medications/vaccinations	•	One month prior to conception to Day 42 post-delivery
Record medically attended AEs ^b until Day 42 post-delivery	•	Mothers: conception to Day 42 post-delivery Infants: birth to Day 42 post-delivery
Record pregnancy outcomes, pregnancy AESIs until Day 42 post-delivery and infant AESIs until Day 42 post-delivery	•	
Infant SAEs from birth until Day 42 post-delivery	•	
Infant MAEs from birth until Day 42 post-delivery	•	
SAEs during pregnancy until Day 42 post-delivery	•	
Record SAEs related to study participation or related to a GSK product ^d	•	
Final Activities		
Study conclusion	•	

• Is used to indicate a study procedure that requires documentation in the individual eCRF.

○ Is used to indicate a study procedure that does not require documentation in the individual eCRF.

^a Contact may be via telephone, SMS, email, video-telephone/telemedicine or other means, depending on local best practice. If the study site is the participant's primary healthcare facility, contact with study personnel may also be made in the context of a visit for routine or event-driven care

^b events reported in the context of routine follow-up or unrelated to the event causing an event-driven visit will not be counted as 'medically attended' (e.g., a minor URI noted in the context of a routine prenatal visit would not be a 'medically attended event')

^c All information needed for retrospective cohort participants can likely be collected on a single day, but it is possible that study personnel may need to re-contact participants to complete/clarify data collection.

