5.1. Inclusion criteria

5.1.1. Retrospective cohort

Adult/Adolescent Participant:

- Adult/Adolescent study participant, from *any of the prior RSV MAT* studies who have either received RSV MAT vaccine or control (placebo, Tdap or influenza vaccine).
- Study participant:
 - Who has reached 2 years+2 months post vaccine/control prior to/at enrollment or
 - who has not reached 2 years+2 months post vaccine/control prior to/at enrollment but is a Woman of Nonchildbearing Potential (WONCBP) as defined in Section 10.3.1.2 at study enrollment, or recipient of bilateral tubal ligation prior to study enrollment.
- Study participant with any pregnancy conceived post-vaccination/control, that has reached Day 42 post-delivery prior to/at enrollment.
- Provide signed and dated informed consent form.
- Be willing to comply with all study requirements and be available for the duration of the study.

Infant Participant:

- Participant live born as the result of a pregnancy followed in an adult/adolescent participant in this study.
- Signed and dated informed consent form obtained from the participant's parent(s)/LAR(s) prior to performance of any study-specific procedure.

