8.4.5.2. Retrospective data source and data collection

For *pregnancies completed (through Day 42 post-delivery) prior to enrollment*, medical data related to pregnancy outcome, pregnancy related AESIs and infant AESIs of any pregnancy conceived post-RSVPreF3 or control vaccination, based on medical records, will be retrospectively collected. ***Data collection will be done through a single structured participant contact to retrospectively collect information about any healthcare received by the mother and infant during pregnancy up to Day 42 post-delivery. This will identify the medical records for review, so that information about any outcome, medically attended event, SAE, or event of special interest is obtained directly from medical records.***

All relevant data collected in the medical records will be recorded in an electronic case report form (eCRF).

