10.1.3. Informed consent process

- The investigator or the investigator's representative will explain the nature of the study, including the risks and benefits, to the participants/participants' parent(s)/LAR(s) and answer all questions regarding the study.
- Potential participants/participants' parent(s)/LAR(s) must be informed that their participation is voluntary. They or their LAR will be required to physically or digitally sign a statement of informed consent that meets the requirements of 21 CFR 50, local regulations, ICH guidelines, Health Insurance Portability and Accountability Act (HIPAA) requirements, privacy and data protection requirements, where applicable, and the IRB/IEC or study center.
- The medical record must include a statement that physical or digital informed consent was obtained before the participant was enrolled in the study and the date the physical or digital consent was obtained. The authorized person obtaining the informed consent must also sign the ICF.
- Participants must be reconsented to the most current version of the ICF(s) during their participation in the study.
- A physical or digital copy of the ICF(s) must be provided to the participant or their LAR.
- *The investigator must obtain assent from the minor participant in addition to the consent provided by the participants' parent(s)/LAR(s) when a minor can assent to participate in a study. The investigator is also accountable for determining a minor's capacity to assent to participation in a research study according to the local laws and regulations.*
- *In accordance with local laws and regulations, participants who become legally emancipated during the study, i.e., reach the legal age of consent, must be reconsented.*
- *The participant must provide consent by signing an ICF, which summarizes the study, includes a consent statement and provides documentation that the participant agrees to continue participating in the study.*
- *If the participant is incapacitated and cannot provide consent, the parent(s)/LAR(s) can provide consent by signing the ICF on their behalf.*

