4.5. Other Safety Analyses

Besides those pregnancy outcomes and AESIs defined in the primary endpoints in Section [4.2.1](#), the other safety data which will be recorded and reported include medically attended AEs, SAEs, SAEs due to study participation, and SAEs related to a GSK product.

The safety analyses will be based on the Maternal Full Analysis Set and Infant Full Analysis Set, with medical records data collection, unless otherwise specified.

Concomitant medications will be coded using the GSKDRUG dictionary. The number and percentage of maternal participants taking concomitant medications up to Day 42 post-delivery will be summarized. A listing will also be provided.

The number and percentage of infants taking concomitant medications/vaccinations from birth up to Day 42 post-delivery will be summarized by group. A listing will also be provided.

Listings and a subset of analysis outputs will be provided to SRT for safety monitoring. The planned outputs are shown in Section 6.3. Other outputs will be provided if deemed necessary.

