4.5.1. Adverse Events

Safety analyses in maternal participants will include summaries by study arms of MAEs, SAEs, SAEs due to study participation, and SAEs related to a GSK product.

Safety analyses in infant participants will include summaries by study arms and gestational age at birth (≥ 37 weeks; <37 weeks; overall) of MAEs, SAEs and SAEs due to study participation.

For MAEs until Day 42 post-delivery (Mothers: conception to Day 42 post-delivery; Infants: birth to Day 42), the number and percentage of maternal or infant participants with each MAE with exact 95% CIs will be tabulated by study arms and displayed by Medical Dictionary for Regulatory Activities (MedDRA) preferred term. By-participant listings will be prepared.

For SAEs and SAEs due to study participation, the number and percentage of participants with each SAE with exact 95% CIs will be tabulated by study arms and by MedDRA preferred term. By-participant listings will be prepared.

The number and percentage of maternal (or infant) participants and maternal pregnancies (based on pregnancies instead of subject) reporting

- at least one MAE
- at least one SAE
- at least one SAEs due to study participation

from study pregnancy conceived up to Day 42 post-delivery (or from delivery up to Day 42 post-delivery for infant participants) with exact 95% CIs will be tabulated by study arms.

A summary of number and percentage of participants with any recorded adverse events by maximum severity will be produced.

A separate summary will be provided for study intervention (administrated from previous RSV MAT studies) related MAEs and SAEs, respectively. A study intervention-related MAE (or SAE) is defined as a MAE (or SAE) for which the investigator classifies the possible relationship to study intervention from previous RSV MAT studies as “Yes”. A worst-case scenario approach will be taken to handle missing relatedness data, i.e. the summary table will include events with the relationship to study intervention as ‘Yes’ or missing.

Summaries of life-threatening and fatal SAEs by PT will also be created.

By participant listings of MAEs, SAEs and SAEs due to study participation will be prepared.

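### Pregnancies already past Day 42 when the woman consents cannot contain a maternal death, yet they stay in the denominator of the maternal fatal-SAE summary

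*Protocol*

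**What the plan says.** **Entry.** The retrospective cohort takes a "Study participant with any pregnancy conceived post-vaccination/control, that has reached Day 42 post-delivery prior to/at enrollment" (Protocol 5.1.1). She must also "Provide signed and dated informed consent form" and "Be willing to comply with all study requirements and be available for the duration of the study". Table 1 places "Maternal and infant informed consent" at Visit 1. Protocol 8.4.5.2 starts ascertainment from the woman herself: "Data collection will be done through a single structured participant contact to retrospectively collect information about any healthcare received by the mother and infant". Footnote b to Protocol Table 2 shows that past pregnancies can also be recorded at Visit 1 in the prospective cohort.

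**Consent by others.** Protocol 10.1.3 covers minors and incapacity: "If the participant is incapacitated and cannot provide consent, the parent(s)/LAR(s) can provide consent by signing the ICF on their behalf". It describes no route for a woman who has died.

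**The event.** Protocol Table 15 defines maternal death as death during pregnancy or within 42 days of its end. The Appendix 6 index marks it as not a study-specific AESI, so it reaches the results only as a fatal SAE.

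**Analysis.** The maternal Full Analysis Set (FAS) pools both cohorts (SAP Table 2). SAP 4.5 states: "The safety analyses will be based on the Maternal Full Analysis Set and Infant Full Analysis Set, with medical records data collection". SAP 4.5.1 tabulates each SAE by arm and preferred term with number, percentage and exact 95% CI, and adds: "Summaries of life-threatening and fatal SAEs by PT will also be created". That fatal-SAE sentence names no percentage, interval or denominator, but SAP 4.1.1 makes number and percentage the default for categorical data. Stratification by cohort is planned for primary and secondary endpoints (SAP 4.6.2.3). For safety summaries, subgroup analysis is left to later judgement (SAP 4.6.2).

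**The concern.** A woman who died in pregnancy or within 42 days of its end, before the study reached her, cannot be enrolled. Every pregnancy that was complete at consent was therefore survived, whatever the true risk. If these women sit in the denominator as women without the event, the pooled figure mixes pregnancies in which death could be observed with pregnancies in which it could not.

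This is a safety follow-up study prompted by a pregnancy-related signal (Protocol 2.2), so a zero or near-zero count of maternal deaths may be read as reassurance. Part of that reassurance would come from how women enter the study. Protocol 4.5 lists self-selection, recall bias and unknown confounding, but not survival to consent, so a reader of the report would not be warned.

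**Working it through.** **Step 1: is the event possible in a completed pregnancy?** Consent comes after Day 42 (Protocol 5.1.1), and the event must fall by day 42 after the pregnancy ends (Protocol Table 15). The two windows do not overlap, so the count is zero by construction. The protocol's own class of ongoing pregnancies runs up to Day 42 post-delivery (Protocol 4.1). Those women are at risk only from consent onward. Only pregnancies conceived after enrolment are observed over the full window.

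**Step 2: reproduce the plan's figures.**
- Planned women with a pregnancy (Protocol 9.5): 2540 × 0.10 × 0.60 = 152 and 5700 × 0.50 × 0.30 × 0.60 = 513. The total is 665, stated as about 650.
- Clopper-Pearson limits (Protocol Table 13): 1/650 gives an upper limit of 0.85% (stated 0.9), 1/300 gives 1.84% (stated 1.8), and 15/300 gives 2.83% to 8.11% (stated 2.8 to 8.1). The method is reproduced.

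**Step 3: bias in the percentage.** Let f be the share of FAS women whose only study pregnancies were complete at consent. If the rate among the others is r, the pooled percentage estimates (1 − f) × r. The documents do not give f. Vaccination stopped on 28 February 2022 (Protocol 2.2) and the assumed start was 7 December 2022 (Protocol 9.5). Every woman therefore had just over nine months before enrolment could begin, and one cohort consists entirely of women with completed pregnancies. So f is unlikely to be trivial, but it cannot be calculated. I show 30%, 50% and 70% as assumptions.

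**Step 4: effect on an exact upper limit with zero deaths.** The two-sided 95% upper limit for 0/n is 1 − 0.025^(1/n).

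| f | n remaining of 650 | upper limit, 0 deaths | one death as a percentage |
|---|---|---|---|
| 0 | 650 | 0.57% | 0.15% |
| 30% | 455 | 0.81% | 0.22% |
| 50% | 325 | 1.13% | 0.31% |
| 70% | 195 | 1.87% | 0.51% |

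Suppose the rate among the remaining women equalled the pooled limit. The chance of seeing no death would then be about 0.025^(1 − f), that is 7.6%, 15.8% and 33.1%, against a nominal 2.5%.

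**Step 5: by arm.** The SAP tables are by arm, so 650 is only an illustrative base. The limit is close to 3.69/n, so removing a share f multiplies it by about 1/(1 − f) at any n. In the protocol's scenario of 100 RSVPreF3 women, 0/100 gives 3.62%. If half were complete at consent, 0/50 gives 7.11%.

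**Step 6: how many deaths to expect.** The documents give no maternal mortality figure. Assuming 20 to 300 per 100,000, 650 pregnancies would yield 650 × 0.0002 = 0.13 to 650 × 0.003 = 1.95 deaths if all could be observed.

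**The case against.** The strongest reply is that no maternal-death rate with a confidence limit is planned. The fatal-SAE sentence in SAP 4.5.1 specifies no interval, and the exact intervals belong to the table of each SAE by preferred term. Protocol 10.2.3.1 asks for the diagnosis to be recorded where possible, so a death would usually appear under its cause, beside non-fatal cases. With no deaths there need be no row at all. This stands. A reader might infer that the SAP will publish a falsely tight upper bound for maternal death on the whole FAS, and the documents do not support that. An interval reaches a fatal event only through its preferred-term row, and only the fatal part of that row is affected.

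The reply also notes that maternal death is neither an AESI nor an endpoint, and that deaths among enrolled women will be seen individually. There are by-participant SAE listings (SAP 4.5.1), a listing of fatal maternal AEs for the safety review team (SAP 6.3.1), and death as a withdrawal reason (Protocol 7.2). This also stands, and it lowers the importance of the point. The pooled limit of 0.57% is about 566 per 100,000, above the top of the range assumed in Step 6, so even that limit would reassure little.

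Finally, cohort stratification might be thought to cover the problem. It does not. It is committed only for primary and secondary endpoints, and the prospective cohort can itself contain pregnancies completed before enrolment.

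**Conclusion.** The structural point holds. Pregnancies past Day 42 at consent are conditional on the woman's survival, and the SAP keeps them in the pooled set used for maternal SAE and fatal-SAE summaries without a committed split or a stated limitation. Any fatal-SAE percentage on that set is biased down by the factor (1 − f). An exact limit for a row made up only of fatal events would be too low by roughly the same factor.

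The size depends on f, which the documents do not give. At an assumed 30% to 70%, the zero-death limit on 650 moves from 0.57% to 0.81–1.87%. The actual tables will rest on smaller numbers, by arm and restricted to women with medical records.

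A reader might also infer that the comparison of RSVPreF3 with control is distorted. Nothing in the documents shows this. It would require survival to consent, or the completed share, to differ by arm. With few or no deaths expected and no endpoint affected, this is a minor correction to safety reporting.

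**What to change.** In SAP 4.5.1, present maternal fatal SAEs by arm in three classes of pregnancy:

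- **(a) Past Day 42 before enrolment:** shown as 'not at risk by design' and left out of the denominator.
- **(b) Ongoing at enrolment:** with a note that the woman is at risk only from consent onward, so this figure is still partly conditional on survival.
- **(c) Conceived after enrolment:** observed over the full window.

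Classify by pregnancy, because one woman may contribute to more than one class. SAP 4.5.1 already plans some tabulations by pregnancy. In Protocol 4.5, add a sentence that pregnancies completed before enrolment are observed only in women who survived to consent.

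The cost is some SAP wording, one limitation sentence and a split that uses dates already collected. The downside is smaller denominators and a less favourable limit.

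I would not extend this to reporting vital status, pregnancy status and cause of death by arm for women who never consented. The tracking described in Protocol 10.1.4 covers pre-screening, screening and projected enrolment, not those items. Collecting them would be a protocol change that raises consent and data-protection questions.

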2. INTRODUCTION

2.1. Study rationale

The study is designed to describe the safety during pregnancies conceived after the prior study vaccination (or control) and to collect all the medically related information in subsequent pregnancies in women who previously were administered RSVPreF3 maternal vaccine or control from any RSV MAT study.

2.2. Background

GSK was developing an investigational Respiratory Syncytial Virus (RSV) vaccine for administration to pregnant women, with the aim of preventing medically assessed, RSV-associated lower respiratory tract illnesses (LRTIs) in their infants by transfer of maternal antibodies. The primary endpoint for efficacy in the development program was their infants' protection from RSV for first 6 months of life. The vaccine candidate is an engineered version of the RSV fusion (F) surface glycoprotein, stabilized in the pre-fusion conformation (RSVPreF3).

Several Phase I to Phase III studies were conducted in pregnant and non-pregnant women; *throughout this document these studies are collectively referenced as the 'prior RSV MAT studies'*. Briefly, these were:

- RSV MAT-001: **RSVPreF3** in non-pregnant women, first time in human, safety and immunogenicity
- RSV MAT-004: **RSVPreF3** first time in pregnant women, safety and dose confirmation
- RSV MAT-010: RSVPreF3 co-administration with influenza vaccination, lot-to-lot consistency
- RSV MAT-011: RSVPreF3 co-administration with Tdap (*Boostrix*) vaccination, second dose of RSVPreF3
- RSV MAT-009: Efficacy in infants of RSVPreF3-vaccinated pregnant women
- RSV MAT-012: RSVPreF3 in high-risk (high-risk adult **women** + healthy adolescents 15-17 years) pregnancies
- RSV MAT-039: RSVPreF3 in healthy non-pregnant girls ages 9-17 years and non-pregnant adult women ages 18-49 years

In all studies, the study participants received one dose of RSV MAT vaccine (or control) except in RSV MAT-011 study, where some participants received a second dose. For participants in MAT-011 study who received a second dose, any pregnancy conceived after first dose will be considered in this study; MAT-011 participants enrolled in the prospective cohort will be followed for pregnancies conceived up to 2 years post last dose. In studies with non-pregnant women, the study participants were followed up to 6 months post-vaccination. In studies including pregnant women, safety of the candidate

vaccine was evaluated in maternal participants for up to 6 months after delivery. Safety in infants was evaluated for up to 12 months after birth. Safety evaluation included assessment of medically attended AEs, serious adverse events, pregnancy outcomes, and pregnancy-related and infant adverse events of special interest (AESIs).

Following review of the data collected from the RSV MAT-009 study in pregnant women, a safety signal was identified. An imbalance in the proportion of preterm births was observed in infants born to vaccinated mothers who received RSV maternal vaccine versus those who received placebo. The safety signal was investigated and based on the above observations, GSK decided to stop enrollment and vaccination for all actively enrolling RSV MAT studies as of 28 February 2022. From this date, no new pregnant or non-pregnant women were enrolled or vaccinated in the studies. Children born to participating pregnant women *who were vaccinated were* continued to be followed-up in these studies. Safety monitoring of all enrolled participants continued during the rest of the study period.

As the *identified* safety signal is pregnancy-related and related to neonatal events, GSK decided to continue to evaluate safety of RSVPreF3 in pregnancies conceived after the prior study vaccination. This current study will enroll women who were enrolled in the RSV MAT-001, RSV MAT-004, RSV MAT-010, RSV MAT-011, RSV MAT-009, RSV MAT-012 or RSV MAT-039 studies and record information about their pregnancies conceived post-study vaccination (if they occur prior to/during the current study period). To clarify, for those enrolled in prior studies of pregnant women (i.e., RSV MAT-004, RSV MAT-009, RSV MAT-012), this study will follow-up the subsequent pregnancies conceived after the *prior* study pregnancy in which RSVPreF3 vaccination (or control) was administered.

2.3. Benefit/risk assessment

No intervention will be administered in this study.

Detailed information about the known benefits and risks and expected AEs of RSV Maternal Vaccine (RSVPreF3) can be found in the IB.

3. OBJECTIVES AND ENDPOINTS

Table 5 Objectives and Endpoints

Objectives	Endpoints
Primary	
To describe the incidence of pregnancy outcomes, pregnancy related adverse events of special interest (AESIs) and infant AESIs during the first pregnancy conceived within 2 years post-vaccination in participants enrolled in RSV MAT studies (by study arm, those previously received RSVPreF3 and control) up to Day 42 post-delivery.	Incidence of pregnancy outcomes, pregnancy related AESIs and infant AESIs during the first pregnancy conceived within 2 years post-vaccination in participants enrolled in RSV MAT studies (by study arm, those previously received RSVPreF3 and control) up to Day 42 post-delivery.
Secondary	
To describe the incidence of pregnancy outcomes, pregnancy related adverse events of special interest (AESIs) and infant AESIs during any pregnancy conceived within 2 years post-vaccination in participants enrolled in RSV MAT studies (by study arm, those previously received RSVPreF3 and control) up to Day 42 post-delivery.	Incidence of pregnancy outcomes, pregnancy related AESIs and infant AESIs during any pregnancy conceived within 2 years post-vaccination in participants enrolled in RSV MAT studies (by study arm, those previously received RSVPreF3 and control) up to Day 42 post-delivery.
To describe the incidence of selected pregnancy outcomes, pregnancy related AESIs and infant AESIs by risk status and by selected risk factors for or causes of those events/outcomes during pregnancies conceived within 2 years post-vaccination in participants enrolled in RSV MAT studies (by study arm, those previously received RSVPreF3 and control) up to day 42 post-delivery.	Incidence of selected pregnancy outcomes, pregnancy related AESIs and infant AESIs by risk status and by selected risk factors for or causes of those events/outcomes during any pregnancy conceived within 2 years post-vaccination in participants enrolled in RSV MAT studies (by study arm, those previously received RSVPreF3 and control) up to Day 42 post-delivery.
	Incidence of selected pregnancy outcomes, pregnancy related AESIs and infant AESIs by risk status and by selected risk factors for or causes of those events/outcomes during the first pregnancy conceived within 2 years post-vaccination in participants enrolled in RSV MAT studies (by study arm, those previously received RSVPreF3 and control) up to Day 42 post-delivery.
Tertiary (Exploratory)	

CCI

